Title	Randomised controlled trial to investigate N-nitrosamine formation after meat intake: protocol for Study 1 of the Nitrate INFORMER Studies (Nitrate INFORMER study: I s N itrosamine F ORMation d Ependent on sou R ce)
Investigators	[name] PhD ^{1,2} , [name] PhD ³ , [name] PhD ³ , [name] PhD ¹ , [name] PhD ^{1,2} , [name] ² , [name] ² , [name] PhD ^{1,2} , [name] PhD ⁴ , [name] PhD ¹ , [name] PhD ⁵ , [name] PhD ^{1,2} , [name] PhD ^{1,2} .
Affiliations	¹ Nutrition and Health Innovation Research Institute, School of Medical and Health Sciences, Edith Cowan University, Perth, Australia ² Medical School, The University of Western Australia, Royal Perth Hospital, Perth, Western Australia, Australia ³ School of Biomedical Sciences, University of Western Australia, Royal Perth Hospital, Perth, Western Australia, Australia ⁴ Centre for Integrative Metabolomics and Computational Biology, School of Medical and Health Sciences, Edith Cowan University, Perth, Australia ⁵ Flinders Centre for Epidemiology and Biostatistics, Flinders University, Adelaide, SA, Australia
Hypothesis	Endogenous N -nitrosamine levels will be higher after ingestion of meat with added nitrate compared to meat without added nitrate.
Aims	Primary aim: To investigate nitrate to N -nitrosamine formation after ingestion of meat with and without added nitrate.
Background and significance	
Nitrate is a controversial component of vegetables, meat, and drinking water. The now well-established benefits of nitrate, through the enterosalivary nitrate-nitrite-nitric oxide (NO) pathway¹, on cardiovascular risk factors and long term cardiovascular disease risk^{2,3} are tarnished by a continuing concern about a link between nitrate ingestion and cancer. This can result in misguided advice to avoid consumption of high-nitrate leafy green vegetables by both the media and the scientific literature. A recent media headline stated, “Cancer alert over rocket: trendy salad leaves exceed safe levels of carcinogenic nitrates in one in every ten samples”. One scientific review stated, “the presence of nitrate in vegetables, as in water and generally in other foods, is a serious threat to man’s health”⁴. Controversy in the literature, and gaps in our knowledge are leading to confusing messages around vegetables that may play a critical role in cardiovascular health.
 
Cancer in relation to nitrate consumption has been a concern among researchers since the 1970’s when it was demonstrated that dietary nitrate had the potential to form carcinogenic N-nitrosoamines^{5,6}. N-nitroso compounds (NOCs) are highly carcinogenic in laboratory animals⁷ and endogenously formed NOCs are associated with cancers in humans, specifically gastric cancer, oesophageal cancer, colorectal cancer and bladder cancer⁸. The International Agency for Research on Cancer/World Health Organization (WHO) has summarized that: “Ingested nitrate or nitrite under conditions that result in endogenous nitrosation is probably carcinogenic to humans (group 2A)”⁹. However, convincing epidemiological evidence for an increased risk of human cancer is still lacking. A review of all studies in 2003 by the Joint Food and Agriculture Organisation (FAO) and WHO Expert Committee on Food Additives (JECFA) found no evidence of an increased risk of cancer with dietary nitrate consumption¹⁰.
 
The major dietary sources of nitrate are vegetables, meat, and drinking water. Nitrate from vegetables accounts for approximately 80% of dietary nitrate intake¹¹. Nitrate, being an important part of the nitrogen cycle, plays an important role in the growth and development of plants. Vegetables such as lettuce, rocket, spinach and beetroot have high concentrations of nitrate while other vegetables, such as peas, tomato and potato have low concentrations of nitrate¹². Meat is a dietary source of nitrate due to


its use as a food additive, primarily to improve the microbiological safety of cured meat and extend its shelf life¹³. Nitrate in drinking water is a contaminant, originating primarily from the agricultural use of fertilizers and manure, as well as wastewater treatment and septic tanks¹⁴. Source of nitrate could be a crucial factor determining whether the consumption of nitrate is linked with beneficial (such as improving cardiovascular health) versus harmful (potentially carcinogenic *N*-nitrosamine formation) effects. One reason for which effects could differ between source is that, unlike meat and water-derived nitrate, vegetables contain high levels of vitamin C and/or polyphenols that may inhibit the production of *N*-nitrosamines¹⁵.

To the best of our knowledge, no study has investigated the formation of *N*-nitrosamines after consumption of the different sources of nitrate in humans. Our overarching objective is to measure *N*-nitrosamine formation after intake of the major sources of nitrate (meat, vegetables, water, or a combination). Currently, guidelines on nitrate intake do not differentiate between dietary sources of nitrate.

The results of these randomised, controlled, cross-over clinical trials will inform international policymakers on safe source-dependent nitrate levels in the environment and diet, particularly the Joint FAO/WHO Expert Committee on Food Additives (JECFA) and European Food Safety Authority (EFSA) guidelines. Currently, EFSA has set the Acceptable Daily Intake (ADI) for nitrate at 3.7 mg/kg (approximately 260 mg for a 70 kg adult), regardless of source¹⁶.

The first of these studies will investigate N-nitrosamine formation after intake of meat with and without added nitrate.

Study setting All Nitrate INFORMER study visits will take place at the Royal Perth Hospital Research Foundation, Nutrition and Health Innovation Research Institute, School of Medical and Health Sciences, Edith Cowan University, Perth, Western Australia.

Participants We will recruit 25 healthy, ambulant, community-dwelling men and women aged between 18 to 70 years old and with no history of major chronic disease, from the Perth general population.

Exclusion criteria. Individuals volunteering to participate in the study will be excluded according to the following criteria: current or recent (<12 months) smoking; body mass index (BMI) <18 or > 35 kg/m²; systolic blood pressure > 160 mmHg ; diastolic blood pressure > 100 mmHg;; any major illness such as cancer, psychiatric illness, diagnosed diabetes; use of any of the following medications: statins, antihypertensives, nitric oxide donors, antithrombotic medication, anti-coagulant medication, anti-arrhythmic drugs, beta-blockers, regular aspirin use, regular proton pump inhibitor use; alcohol consumption > 30g/day; women who are pregnant, lactating, or wishing to become pregnant during the study; use of antibiotics within the previous 12 weeks of the study; regular use of mouthwash and not willing to cease mouthwash use for the duration of the study; participation on other research studies; major GIT condition e.g. Crohn's disease and inflammatory bowel disease; and inability or unwillingness to follow the study protocol.

Recruitment Eligibility to participate in the study will be assessed via a two-step process:

1. **Telephone screening.** A telephone questionnaire will be used to screen volunteers according to the study's inclusion / exclusion criteria. Volunteers who are eligible to participate will be sent an information pack explaining the study in detail and a clinic assessment visit will be scheduled for further physical screening.
2. **Clinic assessment visit.** Prior to commencement of physical screening, volunteers will be required to sign an informed consent form. Physical screening will comprise of anthropometric measurements (height and weight), blood pressure, an electrocardiogram, and a fasting blood test for measurement of lipids (cholesterol, triglycerides, LDL cholesterol and HDL cholesterol) and glucose. Blood pressure will be assessed using a CARES-CAPE™ Dinamap v100 Vital Signs Monitor (GE Health-care, Buckinghamshire, UK). Participants will rest in a supine position for 10 minutes prior to having 5 blood pressure and heart rate measurements performed at 2-minute intervals. The first measurement will be discarded and the mean of the remaining 4 measurements will be used to calculate resting blood pressure.

Study design A crossover study design will be used with a 1-week washout period between interventions. Participants diet for the day before and the day of the intervention will be standardised (food choices on visit 1 will be matched for visit 2) as follows:

For the day before the study visit:

- A choice of 3 breakfasts: cornflakes with milk; rice krispies with milk; white bread toast with eggs.
- Lunch will be provided comprising pumpkin soup and white bread/or rice
- Dinner: a low nitrate vegetarian meal
- All water will be provided
- Participants will be asked to refrain from drinking coffee ¹⁷ and any alcoholic beverage ¹⁸ and do any exercise 24 hours prior to their study visit.

For the day of the study visit:

- Participants will arrive at the study unit fasting
- Breakfast and lunch will comprise the intervention
- Participants will be provided with a standardised dinner: a low nitrate vegetarian meal
- All water will be provided
- Participants will be asked to refrain from drinking coffee ¹⁷ and any alcoholic beverage ¹⁸ and do any exercise for 24 hours from the time of the first intervention.

Dietary interventions

1. *Meat with added nitrate*: 50 g salami and 35 g ham on white bread sandwich at breakfast and lunch.

This intervention will allow us to determine both endogenous formation of *N*-nitrosamines as well as *N*-nitrosamines present in the commercially prepared meat.

2. *Meat without added nitrate*: 65 g Pork mince on white bread sandwich at breakfast and lunch. Nitrate is not an allowed additive in pork mince¹³.

This intervention will allow us to determine if there is endogenous formation of *N*-nitrosamines as well as *N*-nitrosamines present in the prepared meat due to the natural content of nitrate in meat.

3. *Control*: low nitrate vegetable protein burger on white bread. Protein content matched to interventions 1 and 2.

Allocation

Sequence generation. The sequence of intervention allocation will be generated via block randomisation using computer-generated random numbers. Random block sizes of 2 and 4 will be used.

Concealment mechanism. Fifty randomly generated sequences of the interventions for each of the study participants will be printed on separate pieces of paper and sealed in opaque envelopes, numbered 1-50, by a study investigator not involved in performing the intervention, the data collection or the data analysis.

Implementation. Once a participant is deemed eligible and enrolled in the study, the study coordinator will contact the study investigator responsible for randomisation and intervention allocation to obtain the next available envelope and randomly generated intervention sequence.

Blinding

Given the nature of the interventions, participants, and the investigators responsible for delivering the interventions will be unblinded throughout the trial. However, all researchers performing the laboratory analyses and data analyses will be blinded to the interventions that the participants received until after the data analysis has been performed.

Participant timeline

Prior to the first clinic visit, each participant will complete a food frequency questionnaire (FFQ) to assess background habitual diet.

At each clinic visit (**Figure 1**), a baseline urine and faecal stool sample will be collected for measurement of *N*-nitrosamines. Prior to the intervention participants will be instructed to void their bladder into baseline urine collection container. After the first intervention all urine for the subsequent 24-hour period will be collected for measurement of *N*-nitrosamines, nitrate, and nitrite. A faecal stool will be collected for measurement of *N*-nitrosamines, nitrate, and nitrite.

[figure not shown]

Figure 1: Schematic representation of study day timeline

Outcomes *Primary outcomes*

Level of *N*-nitrosamines (*N*-Nitrosodimethylamine, NDMA; *N*-Nitrosomethylethylamine, NMEA; *N*-Nitrosodiethylamine, NDEA; *N*-Nitrosopiperidine, NPIP; *N*-Nitrosomorpholine, NMOR) in urine and faecal stool post intervention.

Assessments **Urine and faecal stool collection.** A urine sample will be collected at baseline, and from intervention up until 24 hours post-intervention. For the baseline sample, participants will be provided with a sterilized container and instructions to discard the first urine sample of the day and then collect all urine until the intervention which will be brought into the clinic. Participants will be instructed to drink 250 ml water on waking, For the 24-hour urine samples, participants will be provided with sterilized containers and instructions to collect all urine until 24 hours post intervention. Urine aliquots will be frozen at -80°C until analysis. A stool sample will be collected at baseline and for the 24 hour period post the first intervention. Participants will be provided with instructions and a stool sample collection pack (collection bags, cable ties, large zip lock bags, freezer ice blocks and a designated cooler bag for transport). Collected stool samples will be weighed and frozen at -80°C until analysis.

***N*-nitrosamines.** Nitrosamines in the interventions, urine and stool samples will be measured by gas chromatography mass spectrometry (GCMS). Volatile nitrosamines will be extracted with dichloromethane and are well separated by gas chromatography. Identification will be by retention time and unique molecular ions for each of five common nitrosamines (**Table 1**). Quantitation will be made

by using deuterium labelled internal standards, *N*-nitrosodimethylamine-D6; *N*-nitrosodiethylamine D10; *N*-nitrosomorpholine D8 (Cambridge Isotopes) and *N*-nitrosopiperidine D10 (Toronto Research Chemicals). The most commonly detected nitrosamines are NDMA and *N*-Nitrosopiperidine (NPIP). Control experiments in which water stored in the same containers as those used for sample collection and storage will be performed to test for any leaching of volatile nitrosamines.

Table 1: *N*-nitrosamines that will be analysed by GCMS

N -Nitrosamine	Abbreviation	M+ ion (m/z)
N -Nitrosodimethylamine	NDMA	74.05
N -Nitrosomethylethylamine	NMEA	88.06
N -Nitrosodiethylamine	NDEA	102.08
N -Nitrosopiperidine	NPIP	114.08
N -Nitrosomorpholine	NMOR	116.06

Sample size and power

Sample size is based on a crossover design and the primary outcome of *N*-nitrosamines, specifically *N*-Nitrosodimethylamine (NDMA) in urine. At $\alpha=0.05$, 2 measures per subject (baseline and post) and a correlation of $\rho=0.6$ between measures, 25 participants will provide 80% power to detect a 0.6 SD increase in NDMA concentration. To allow for a 10% withdrawal rate, we plan to recruit 25 participants into the study. A rolling recruitment of participants will be performed until the sample size is reached.

Statistical methods

Statistical analyses will be performed using IBM SPSS Statistics for Windows, version 25 (IBM) and STATA/IC 17.0 (StataCorp LLC). Descriptive statistics of normally distributed continuous variables will be expressed as mean (\pm standard deviation, SD), non-normally distributed continuous variables as median (interquartile range, IQR) and categorical variables as number (proportion, %). Data will be assessed for outliers and normality prior to analysis. Non-normally distributed data will be log transformed if necessary. Treatment effects for outcomes will be obtained using linear mixed models including baseline measurements, treatment order, period, and time (as a categorical variable) as fixed effects. We will also include a treatment X period interaction term to assess for possible treatment-period interactions and we will separately assess for carryover effects with dummy variables to indicate the previous treatment. Treatment effects for outcomes with a single post-intervention measurement will be obtained using linear mixed models including baseline measurements, treatment order, and period as predictors. The subject ID number will be included as a random intercept in each model. An overall 2-sided type-1 error rate of $P<0.05$ will be used to assess statistical significance for all hypothesis testing.

References

1. Lundberg JO and Weitzberg E. NO-synthase independent NO generation in mammals. *Biochem Biophys Res Commun.* 2010;396:39-45.

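### The hypothesis concerns endogenous N-nitrosamines, but the planned contrast estimates a difference in total levels and cannot alone support a conclusion about endogenous formation

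*Combined protocol and SAP*

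**What the plan says.** All references are to the combined protocol and SAP.

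- **Hypothesis.** Endogenous N-nitrosamine "levels will be higher after ingestion of meat with added nitrate compared to meat without added nitrate". The primary aim likewise speaks of formation from nitrate.
- **Dietary interventions.** Arm 1 is "50 g salami and 35 g ham on white bread sandwich at breakfast and lunch". The plan says this arm shows endogenous formation and also "nitrosamines present in the commercially prepared meat". Arm 2 is "65 g Pork mince on white bread sandwich at breakfast and lunch", and it too is said to reflect "nitrosamines present in the prepared meat due to the natural content of nitrate in meat". The control is a vegetable-protein burger.
- **Outcomes.** The primary outcome is the level of five N-nitrosamines "in urine and faecal stool post intervention", with no restriction to endogenous origin.
- **Assessments.** Nitrosamines are to be measured in the intervention foods as well as in urine and stool. Baseline samples are taken before the intervention.
- **Statistical methods.** Treatment effects come from mixed models with baseline, treatment order, period and, where relevant, time. There is also a treatment-by-period term, carryover dummies and a random intercept for subject. Food nitrosamine content does not appear.

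**The concern.** The plan itself names two sources for what it measures, while its hypothesis concerns only one of them. It plans the measurement that could help tell them apart, then states no analytic step that uses it.

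If the cured meat delivers more preformed nitrosamine than the mince, a significant contrast could be reported as endogenous formation when there is none. If the mince delivers more, the contrast could understate real formation. The analysis as written does not distinguish these cases.

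The distinction matters for use of the results. The background says the trials are meant to inform international bodies on safe nitrate levels by source. Nitrosamine formed in the body from ingested nitrate, and nitrosamine eaten ready-made, carry different messages for that purpose.

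**Working it through.** **Can any planned element separate the two sources?**

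- *Baseline adjustment:* no. Baseline samples precede the meal, so they cannot carry what arrives with it.
- *Randomisation, crossover, order, period and subject terms:* no. Portions are fixed by arm, so the preformed load is part of the treatment and moves with it.
- *Vegetable-protein control:* no. It contains no meat, so it does not isolate preformed meat nitrosamine.
- *Urinary and faecal nitrate and nitrite:* no. They do not identify the origin of a nitrosamine.
- *Food assays:* potentially yes, but no stated model or calculation uses them.

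Equal loads cannot be assumed. Arm 1 gives 50 + 35 = 85 g of meat per meal and arm 2 gives 65 g. This does not say which arm carries more nitrosamine.

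Even equal loads are not always harmless. On untransformed amounts, with equal recovery from both foods, equal loads cancel. Statistical methods allows a log transformation, and there they do not. With invented endogenous amounts of 2 and 1 the ratio is 2.0; adding 1 to each gives 3/2 = 1.5.

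**The plan's own figure.** Sample size and power gives 25 participants for 80% power at 0.6 SD, α = 0.05 and ρ = 0.6 between baseline and post. Using n = (1.960 + 0.842)² × V / 0.6²:

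- V = 2(1 − 0.6) = 0.8 gives 17.4, so 18 (20 by the t distribution). Power at 25 is 90%.
- V = 1, which reads 0.6 SD as 0.6 SD of the differences, gives 21.8, so 22. Then 22/0.9 = 24.4, so 25.

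The plan's 25 is not reproduced with ρ as written, but it is under the second reading. That is a separate matter. It bears on this point only because the variance of the between-meat contrast is uncertain, so several values are shown.

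**Illustration.** Every shift here is assumed. Let the endogenous difference be zero and let s be the recovered preformed difference, in SD of the outcome. The chance of a significant higher result is the upper-tail rejection probability of a paired t-test, from a noncentral t with n − 1 degrees of freedom and noncentrality s√n/√V. For example, s = 0.4, n = 25 and V = 0.8 give 0.4 × 5/0.894 = 2.24. Against a critical value of 2.064 on 24 degrees of freedom, the probability is 0.574.

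| V (SD²) | Basis | s = 0 | 0.2 | 0.4 | 0.6 |
|---|---|---|---|---|---|
| 0.8 | 2(1 − 0.6): 0.6 taken as the between-visit correlation, which the plan does not state | 2.5% | 19% | 57% | 90% |
| 1.28 | 2(1 − 0.6²): baseline-adjusted, no correlation across periods | 2.5% | 13% | 40% | 72% |
| 2.0 | no between-visit correlation, no baseline adjustment | 2.5% | 10% | 27% | 53% |

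The table uses n = 25. With 22 completers (25 × 0.9 = 22.5, rounded down), the last three columns become 17/52/85%, 12/35/66% and 9/24/48%. A negative shift would act the other way and hide a real endogenous difference.

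**The case against.** The strongest reply is that the authors saw the issue. They name both sources for each meat arm and commit to assaying the foods, so the data needed to qualify the conclusion will exist. The randomised contrast also remains valid for total levels.

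All of that stands. It limits the point to interpretation and to a missing analytic step. It does not remove the point: measuring the foods is not analysing them, and a method chosen after the results are known is no longer pre-specified.

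A second reply is that the illustration is not evidence about this trial. That also stands. The shifts are assumed, and the 90% figure needs both the largest of them and the smallest variance.

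A third is that any correction for preformed intake rests on recoveries the documents do not give, and can have little power. This is a fair reason to keep such an analysis supportive and optional. It is no reason to leave the primary conclusion worded as endogenous.

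**Conclusion.** The point holds. The planned contrast estimates the difference in total N-nitrosamine levels between the two meats. No part of the stated analysis turns that into a statement about endogenous formation, although the hypothesis is worded as one. This follows from the text and does not depend on the sample-size figure or the illustration.

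The size and direction of any bias are unknown. On the assumed shifts, the chance of a significant higher result with no endogenous difference runs from 10% to 90% at n = 25, against 2.5% with no preformed difference.

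A reader might infer more than this, and the documents do not support it:

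- That the authors overlooked preformed nitrosamines. They name them and plan to assay the foods.
- That the contrast is known to be inflated. No food content or recovery is given, and the mince could carry more.
- That equal loads would settle the matter. That needs untransformed amounts and equal recovery from both foods.
- That the trial comparison is invalid. It is valid for total levels.

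**What to change.** 1. State the primary contrast and its conclusion as total N-nitrosamine levels. Do not attribute a positive result to endogenous formation from that contrast alone.
2. Report the assayed nitrosamine content of each food as served beside the contrast. Do so after the blinded analysis: analysts "will be blinded to the interventions that the participants received until after the data analysis has been performed", and food values could reveal the codes.

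These two steps need only wording and assays already planned. Their cost is a primary conclusion narrower than the stated hypothesis.

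**Optional.** Pre-specify a supportive analysis for each nitrosamine. Compare the untransformed between-meat difference in 24-hour excreted amount (urine concentration × volume, plus stool concentration × weight) with the assayed intake difference multiplied by assumed recoveries from 0 to 100%. Use post-intervention amounts, because for baseline urine participants "discard the first urine sample of the day and then collect all urine until the intervention", which gives no 24-hour baseline amount. State that recovery is assumed similar for both foods, carry food and assay variation into the interval, and say how non-detects and participants with no stool in the window are handled.

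This option costs more: a recorded urine volume, five analytes, and low power at high assumed recovery. With a true endogenous difference E = 0.6 SD, recovered shift s and true recovery r, the mean tested at 100% assumed recovery is E + s − s/r. At r = 0.5 and s = 0.2, 0.4, 0.6 SD the mean is 0.4, 0.2, 0. Power at n = 25 is then 57/19/2.5% (V = 0.8) or 27/10/2.5% (V = 2.0). At r = 0.25 it is 2.5% or less. Assuming too low a recovery errs the other way. With no endogenous difference, r = 0.5 and 25% assumed, the mean is s − 0.25 × s/0.5 = s/2, and false higher results occur in 8/19/36% (V = 0.8) or 5/10/17% (V = 2.0). The whole range should therefore be shown, with no single recovery used as the gate. These figures are only a guide, since the variance of urine-plus-stool amounts is not known.

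### The sample-size paragraph uses 25 both as the number giving 80% power and as the number recruited to allow for 10% withdrawal, and the 80% cannot be derived from the stated inputs alone

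*Combined protocol and SAP*

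**What the plan says.** All of the following is in the combined protocol and SAP.

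- **Sample size and power, basis.** "Sample size is based on a crossover design and the primary outcome of" *N*-nitrosamines, specifically NDMA in urine. The inputs are alpha 0.05, "2 measures per subject (baseline and post) and a correlation of" 0.6 between them.
- **Sample size and power, result.** "25 participants will provide 80% power to detect a 0.6 SD increase in NDMA concentration".
- **Sample size and power, withdrawal.** "To allow for a 10% withdrawal rate, we plan to recruit 25 participants into the study". The paragraph ends: "A rolling recruitment of participants will be performed until the sample size is reached".
- **Participants.** "We will recruit 25 healthy, ambulant, community-dwelling men and women".
- **Allocation (concealment).** "Fifty randomly generated sequences of the interventions for each of the study participants" are to be placed in numbered envelopes.
- **Statistical methods.** All tests are two-sided at 0.05. Outcomes with one post-intervention measurement are analysed by "linear mixed models including baseline measurements, treatment order, and period as predictors", with a random intercept for subject.
- **Hypothesis.** The comparison is between meat with and meat without added nitrate.
- **Study design and Dietary interventions.** Three interventions are listed, but only visits 1 and 2 are mentioned.

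**The concern.** The same number is given before and after an allowance for withdrawal, so one of the two sentences must be wrong or incomplete. The Participants section repeats 25 as the recruitment figure and does not settle which is meant.

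Two further gaps make it hard to work out what was intended. The paragraph does not say whether 0.6 SD is in SDs of NDMA between people, of a within-person difference, or of a residual. It also claims a crossover basis while labelling its two measures as baseline and post, which describes a change within one visit and not the comparison of two meats named in the hypothesis.

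This paragraph is the only justification of the sample size. A reader cannot tell from it how many completers the trial needs, or whether the stated power applies to the hypothesis.

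**Working it through.** **Inputs from the protocol:** alpha 0.05 two-sided, effect 0.6 SD, rho 0.6 (baseline with post), 25 participants, power 80%, withdrawal 10%.

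**1. Withdrawal**

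- If 25 completers are needed: 25 / 0.9 = 27.8, so 28 recruits.
- If 25 are recruited: 25 × 0.9 = 22.5, so about 22 complete.

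**2. Attempts to reproduce 80% at 25**

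The standardised effect is dz = 0.6 / (SD of the analysed difference, in SDs of NDMA). Power is from the noncentral t with n − 1 degrees of freedom.

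*(a) Baseline versus post, 0.6 SD of NDMA, rho used.* SD of the difference = √(2(1 − 0.6)) = 0.894, so dz = 0.671. For 80% power, 20 are needed. Power is 90% at 25 and 85% at 22.

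*(b) 0.6 taken as SDs of the paired difference.* dz = 0.6 and rho plays no part. For 80% power, 24 are needed. Power is 82% at 25 and 77% at 22. By normal approximation the requirement is ((1.960 + 0.842) / 0.6)² = 21.8, so 22, and 22 / 0.9 = 24.4, so 25.

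*(c) Baseline-adjusted difference between the two meats, 0.6 SD of NDMA, rho used.* This is closest to the hypothesis and the planned model, but it needs correlations that the protocol does not give. Assume equal SDs. Let r be the correlation of baseline with baseline, and of post with post, across visits; let c be that of baseline at one visit with post at the other. Then

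variance of the adjusted difference = 2[(1 − r) − (0.6 − c)² / (1 − r)].

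| Assumed r, c | SD of adjusted difference | dz | Paired-t power at 25 |
|---|---|---|---|
| 0, 0 | √1.280 = 1.131 | 0.530 | 72% |
| 0.4, 0.4 | √1.067 = 1.033 | 0.581 | 79.6% |
| 0.46, 0.46 | √1.007 = 1.004 | 0.598 | 82% |
| 0.4, 0.2 | √0.667 = 0.816 | 0.735 | 94% |
| 0.4, 0.6 | √1.200 = 1.095 | 0.548 | 75% |

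Estimating the baseline slope and period costs a little power. In simulation with two conditions and n − 3 degrees of freedom, an effect of 0.60 adjusted SD gave 79.7% at 25. With r and c equal, the stated 80% at 25 is therefore recovered at about 0.4 (simple paired t) to 0.46 (slope and period estimated).

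**3. Detectable difference at 80% power (paired t)**

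- 22 completers: 0.626, or 0.63 SD of the within-person difference.
- 25 completers: 0.584, or 0.58 SD.

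**The case against.** The strongest defence on withdrawal is that dropouts are replaced. Recruitment continues until the sample size is reached, and fifty sequences are prepared for 25 participants. That is possible, but the protocol nowhere says so, and replacement would make the sentence about allowing for 10% withdrawal unnecessary.

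The strongest defence of the 80% is reading (c): a two-sided crossover analysis that uses rho = 0.6 does give about 80% at 25 for plausible between-visit correlations. This stands. A reader might infer that the stated power is wrong; the documents support only that an input or a definition is missing.

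Three other inferences go too far:

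- *The trial is underpowered for the hypothesis.* The 72% in reading (c) rests on zero correlation between visits, which is as much an assumption as 0.46.
- *The first 25 is a slip for 22.* The arithmetic in (b) fits, but only by discarding the stated rho and using a normal approximation.
- *Recruitment must rise to 28.* That follows only if the sponsor needs 25 completers and does not replace withdrawals.

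**Conclusion.** The point holds in two parts.

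First, as written there is no withdrawal allowance. This rests only on the protocol's own 25 and 10%: the gap is three recruits (28 against 25), or about 22 completers where 25 are said to be needed, unless withdrawals are replaced.

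Second, 80% at 25 is not derivable from the stated inputs alone. The readings that add no further input give 90% (rho used) or 82% (rho unused). About 80% is reached for the two-meat comparison only by adding between-visit correlations, and other assumed values move the result in either direction. The SD and the powered contrast are undefined.

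The practical effect is modest. If 22 complete, the detectable difference is 0.63 SD of the within-person difference, against 0.58 SD with 25. These two figures assume a paired t-test and that each completer has both meat conditions. This should be fixed, but it is not evidence that the trial is too small.

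**What to change.** Amend the Sample size and power paragraph to state:

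- which number is evaluable and which is recruited;
- whether withdrawals are replaced;
- which SD the effect is measured in;
- which contrast is powered;
- every correlation used (baseline with post within a visit, between visits, and baseline at one visit with post at the other), shown as a range where assumed.

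If recruitment stays at 25 without replacement, wording such as this would do:

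> 25 participants will be recruited; with 10% withdrawal about 22 are expected to complete both meat conditions. With 22 completers, two-sided alpha 0.05 and 80% power, the detectable within-person difference in urine NDMA between meat with and without added nitrate is 0.63 SD of that difference (paired t-test).

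If withdrawals are replaced so that 25 complete, the figure is 0.58 SD.

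A baseline-adjusted figure is best left out for now. About 0.65 SD of the adjusted difference is detectable at 22 when slope and period are estimated, but only in a two-condition analysis. A simulated joint analysis of three conditions, with common error variance and no interaction, gave 83% power at 0.65. The three listed interventions and the two mentioned visits must be reconciled first.

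The cost is protocol wording. No extra participants are required unless the sponsor decides that 25 must complete. The downside is that the stated figure may become slightly less favourable.
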